## **Objectives**

1. Primary: To discover the incidence of abnormal glucose levels after fasting and bowel preparation for colonoscopy in type 2 diabetes subjects.

2. Secondary

- ① Find out the risk factors for abnormal glucose levels
- ② Find out if self-treatment is sufficient to treat hypoglycemia which occurs during fasting and bowel preparation.

## **Background**

Diabetes is rapidly increasing, with about 11% (5.5 million) of the Korean population expected to be diabetic in 2030. Diabetes is a known risk factor for colorectal cancer and diabetes patients are recommended to undergo routine colonoscopic surveillance. Colonoscopy requires fasting and bowel preparation, however, their effects on glucose levels have not been investigated.

Subjects normally undergo 14-20 hours of fasting before colonoscopy. In diabetes patients, 14-17 hours of fasting reduces plasma glucose by 20-40%, which increases the risk of hypoglycemia. Furthermore, subjects are instructed to forgo taking antidiabetic medications during fasting, which may induce hyperglycemic crisis or abnormal glucose levels due to Dawn phenomenon or Somogyi effect. Dehydration during bowel preparation may also increase the risk of abnormal glucose levels. In diabetic patients, autonomic dysfunction may reduce recognition of hypoglycemic symptoms, increasing risk of catastrophic events.

In diabetic patients who underwent ophthalmologic procedures after 8 hours of fasting, hypoglycemia has been reported in 3% and hyperglycemia in 2.4%. One study which investigated abnormal glucose responses in diabetes patients who underwent colonoscopy found a hypoglycemic rate of 20%. Therefore, we aim to investigate the occurrence of abnormal blood glucose levels in diabetes patients during colonoscopy preparation.

## **Subjects**

1. Inclusion criteria: Type 2 diabetes subjects between the ages of 20-75 who have colonoscopy performed at the endoscopy center of International St. Mary's Hospital.

2. Exclusion criteria

- ① Type I diabetes patients
- ② Those who have not completed colonoscopy preparation
- ③ Those who have not met the fasting requirements
- ④ Patients with known ongoing infection
- ⑤ Patients with known cancer, undergoing current treatment

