## **Subject numbers**

The incidence of abnormal glucose levels is expected to be between 5 to 10%. 50 positive subjects are required for multivariable analysis, therefore 1000 subjects should be included in this study.

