## 2. Confirmation of diabetes

- ① Diabetes history will be rechecked by a trained nurse who is blind to the study at the preparation room of the endoscopy center.
- ② Subjects will fill out a questionnaire and have their plasma glucose checked while awaiting colonoscopy.

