## 3. Treatment of abnormal glucose levels

- ① Hypoglycemic patients with a glucose level  $< 70\text{mg/dL}$  will be given 5% dextrose water.
- ② Hyperglycemic patients with a glucose level  $> 250\text{mg/dL}$  will be given normal saline.
- ③ Treated subjects will be discharged after confirmation of glucose level restoration to normal values.

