## Study variables

1. Age, gender
2. Amount and total time of colonoscopy preparation. Total fasting time. Time from last antidiabetic medication taken to colonoscopy.
3. Diabetes history (years), Diabetes treatment method (exercise/diet, oral medication, methods including insulin), other injected agents, previous history of hypo/hyperglycemia, hypoglycemia awareness
4. Plasma glucose level before colonoscopy

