## Statistical Analysis

Primary endpoint: Percentage of study subjects with hypo or hyperglycemia

Secondary endpoint

- ① Risk factors of hypo/hyperglycemia
- ② Effect of hypoglycemia self-treatment

Verify the risk factors using T test the  $X^2$  test.

Identify the odds ratios of risk factors by univariable and multivariable analysis.

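### Read literally, inclusion depends on the colonoscopy taking place, which comes after the glucose outcome and could remove abnormal readings from the primary percentage

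*Combined protocol and SAP*

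**What the plan says.** The combined protocol and SAP bears on this point in six places.

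- **Objectives.** The primary aim is the "incidence of abnormal glucose levels after fasting and bowel preparation for colonoscopy". The target is defined by the preparation.
- **Subjects, inclusion criteria.** Subjects are those aged 20-75 with type 2 diabetes "who have colonoscopy performed at the endoscopy center" of the hospital. Exclusions 2 and 3 separately remove people who did not complete the preparation or did not meet the fasting requirements.
- **Study design, 2. Confirmation of diabetes.** Subjects "have their plasma glucose checked while awaiting colonoscopy".
- **Study variables.** The outcome variable is listed as "Plasma glucose level before colonoscopy". No variable records whether the procedure was performed, postponed or cancelled.
- **Study design, 3. Treatment of abnormal glucose levels.** After the treatments for low and high readings, the section closes: "Treated subjects will be discharged after confirmation of glucose level restoration to normal values". It does not mention the colonoscopy.
- **Statistical Analysis.** The primary endpoint is the "Percentage of study subjects with hypo or hyperglycemia". No analysis set is defined beyond that, so the inclusion criterion fixes the denominator.

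**The concern.** Eligibility is normally settled before the outcome is known, or at least independently of it. Here the criterion, taken at its word, refers to an event that follows the outcome measurement. Someone who fasted, finished the preparation and had glucose measured, but was not scoped, fits the primary objective and fails the inclusion criterion.

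If the reason for not being scoped is unrelated to glucose, the study loses a few subjects and the percentage is not distorted. If the reason is the reading itself, the loss is selective: a positive subject disappears from numerator and denominator, and the percentage falls. A larger sample would not reduce that bias. Fewer positives would also remain for the risk-factor model, for which the plan sets a requirement: "50 positive subjects are required for multivariable analysis".

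Because procedure status is not among the study variables, the planned data could not show afterwards whether such losses occurred.

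**Working it through.** **Inputs from the documents.** Expected incidence of 5% to 10%, 50 positive subjects required, and 1000 subjects planned (all from Subject numbers). The outcome is measured before the procedure (Confirmation of diabetes; Study variables).

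**Inputs that are assumed.** The documents give no rate at which measured subjects go unscoped. Let *c* be the share of abnormal subjects lost and *d* the share of normal subjects lost. I take *d* = 0 and let *c* run over 5%, 10%, 20% and 50%. These values illustrate the effect and estimate nothing.

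**Step 1: the plan's own figure.** Required positives divided by incidence: 50 / 0.05 = 1000, which matches the plan. At the upper end of the range, 50 / 0.10 = 500. The plan is therefore sized for the lower incidence. At exactly 5%, the binomial probability of at least 50 positives among 1000 is about 0.52, so at that incidence there is no reserve.

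**Step 2: the effect of losing measured subjects.** With true incidence *p*,

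observed = p(1 − c) / [p(1 − c) + (1 − p)(1 − d)].

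If c = d, this reduces to *p* and there is no bias. The percentage falls only when c exceeds d. With d = 0 it becomes p(1 − c) / (1 − pc).

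| Assumed c | Observed, true 5% | Shift (points) | Observed, true 10% | Shift (points) |
|---|---|---|---|---|
| 5% | 4.76% | 0.24 | 9.55% | 0.45 |
| 10% | 45/995 = 4.52% | 0.48 | 90/990 = 9.09% | 0.91 |
| 20% | 40/990 = 4.04% | 0.96 | 80/980 = 8.16% | 1.84 |
| 50% | 25/975 = 2.56% | 2.44 | 50/950 = 5.26% | 4.74 |

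The fractions are per 1000 subjects measured.

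**Step 3: comparison with sampling error.** The 95% half-width is 1.96 × √(p(1 − p)/1000), which is 1.35 points at 5% and 1.86 points at 10%. At a true 5%, a 10% loss shifts the result by about a third of the half-width (0.48 / 1.35), and a 20% loss by about seven tenths (0.96 / 1.35). Only the 50% assumption exceeds it.

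**Step 4: effect on the event count.** At a true 5%, 1000 measured subjects yield 45 counted positives with c = 10% and 40 with c = 20%. To expect 50, the study would need to measure 50 / 0.045 = 1112 (rounded up) or 50 / 0.040 = 1250 subjects.

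**Step 5: after the fix.** If every prepared, measured and otherwise eligible subject is counted, the observed percentage equals *p*, and the planned 1000 still gives 50 expected positives at 5%. The sample size does not change.

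**The case against.** The strongest reply is that nothing in the documents says a procedure is ever called off because of a reading. Without such cases there is no selective loss and no bias. This stands, and it makes the concern conditional.

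The inclusion wording can also be read more loosely. In a forward-looking plan it may simply describe people coming for colonoscopy. The colonoscopy preparation section speaks of subjects scheduled for the procedure, and both that section and the confirmation section call them subjects before any procedure has happened. On this reading a measured subject who is later postponed stays in. The reading is reasonable, but the inclusion criterion is the operative rule and uses different words. Two tenable readings that give different denominators for the primary endpoint are enough reason to settle the sentence.

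A reader might infer from the treatment section, which goes from treatment to discharge, that abnormal subjects are sent home unscoped. The text does not support that. The section covers treatment and the condition for discharge, and does not set out the order of the visit. Discharge after a completed colonoscopy fits it equally well.

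A reader might also infer that the risk-factor analysis would lose its most informative cases. The plan analyses hypo- or hyperglycemia as present or absent, so a severe case counts the same as a mild one. Lost cases would lower the event count. Distortion of the odds ratios would further require that lost cases differ from retained ones in their risk factors, and the documents say nothing on that.

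**Conclusion.** The mismatch is real and needs no assumed rate. Followed literally, the inclusion rule depends on an event that comes after the outcome and is not part of the primary objective, and it drops a fully prepared and measured subject who is not scoped.

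It would go too far to conclude that the planned incidence is understated. Downward bias follows only if some procedures do not take place and abnormal subjects are affected more often than normal ones. The documents neither state nor rule this out, and they give no rate. Under the assumption that 10% or 20% of abnormal subjects and no normal ones are lost, a true 5% would read 4.5% or 4.0%. Those shifts are within the half-width of about 1.35 points at 1000 subjects, but they act in one direction and do not shrink with sample size.

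The point is worth correcting because the change is nearly free and removes a possible one-way selection on the primary outcome.

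**What to change.** Reword the inclusion criterion along these lines:

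> Type 2 diabetes subjects aged 20-75 who attend the endoscopy center for a scheduled colonoscopy after completing fasting and preparation and have the pre-colonoscopy plasma glucose measured, whether or not the colonoscopy is then performed.

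Keep exclusions 2 and 3 as they stand. The criterion should refer to completing, not merely starting, fasting and preparation, so that it agrees with them.

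Add one field to Study variables for procedure status (performed, postponed or cancelled) with the reason. State in Statistical Analysis that all measured eligible subjects count in the primary denominator, and report how many were measured but not scoped.

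The cost is one reworded criterion, one data field, a sentence on the denominator, and a few subjects without a procedure record. The questionnaire and glucose reading are already taken beforehand, so the measurement itself needs no extra work. The change concerns only who is counted; no rule on proceeding with or cancelling a procedure is proposed.

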## **Study design**

1. Colonoscopy preparation

- ① Subjects will be instructed to fast from 6pm of the day before colonoscopy.
- ② Subjects will be instructed to abstain from diabetes medication while the subjects fast.
- ③ Subjects who are scheduled to undergo colonoscopy in the morning will take colonoscopy preparation medication (2L (liter) of polyethylene glycol with ascorbic acid) in a split dose (i.e. 1L from 8-10 pm of the day before colonoscopy and 1L 4-6 hours before colonoscopy). Those who will undergo colonoscopy in the afternoon will take 2L of the preparation medication 6 hours before colonoscopy.

- ④ Subjects will be instructed to take the preparation medication at rate of 250 mL every 10 to 15 minutes.

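### Exclusions 2 and 3 can drop the subjects that the self-treatment objective needs, and the listed variables do not record who those subjects are

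*Combined protocol and SAP*

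**What the plan says.** Objectives lists as its second secondary aim: "Find out if self-treatment is sufficient to treat hypoglycemia which occurs during fasting and bowel preparation". Statistical Analysis carries this forward as the endpoint "Effect of hypoglycemia self-treatment", with no definition, denominator or method. The methods given there concern risk factors: t and chi-square tests, then "Identify the odds ratios of risk factors by univariable and multivariable analysis".

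Subjects includes patients "who have colonoscopy performed at the endoscopy center" and excludes "Those who have not completed colonoscopy preparation" (exclusion 2) and "Those who have not met the fasting requirements" (exclusion 3). Neither exclusion has an exception.

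The only fasting rule is in Study design, under colonoscopy preparation: "Subjects will be instructed to fast from 6pm of the day before colonoscopy". The same list has morning patients drink the preparation as "1L from 8-10 pm of the day before colonoscopy and 1L 4-6 hours before colonoscopy", which falls within that fast.

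Study variables covers the quantity and duration of preparation, fasting time, medication timing, diabetes history and treatment, past hypo- or hyperglycemia, hypoglycemia awareness and one glucose value before colonoscopy. A questionnaire is mentioned under the confirmation of diabetes, but its items are not shown.

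**The concern.** Exclusions 2 and 3 look like eligibility criteria, but they can be judged only once the fast and preparation are under way. A subject who becomes hypoglycemic may take something for it, or may stop the preparation. Either act may then be the reason for exclusion. The second secondary objective is about exactly these subjects.

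The listed data would not repair the loss. Fasting time and preparation quantity may reveal that a deviation occurred, but not why. The single glucose value is taken on arrival, so it cannot show that someone who has since recovered was ever hypoglycemic.

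At stake is whether this objective can be answered at all and, if it can, whether the answer comes from a group selected by the event being studied.

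**Working it through.** **1. The plan's own figure.** Subject numbers asks for 50 positive subjects at an expected incidence of 5% to 10%. 50 / 0.05 = 1000, which reproduces the stated size (50 / 0.10 = 500 at the other end). This size serves the risk-factor model. Nothing in it was set for the self-treatment objective.

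**2. What decides exclusion 3.** Subjects drink the preparation during the fast, so intake by mouth alone cannot be the test of a breach. No other test is given. Two readings are possible:
- Lenient (for example, a minimum fasting duration): a subject who took something for symptoms may stay in, and none need be lost.
- Strict (anything taken by mouth other than the preparation is a breach): every subject who self-treated by mouth goes.

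Exclusion 2 acts less directly. It removes only those whose preparation was left unfinished.

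**3. How many self-treaters there could be.** The documents give no self-treatment rate. Expected number = 1000 × hypoglycemia incidence × share who self-treat. The share is assumed to be 50%. The 3% and 20% incidences are the Background figures. The 5% and 10% are the Subject numbers range, which covers hypo- and hyperglycemia together and so is a generous input for hypoglycemia alone.

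| Hypoglycemia | Self-treaters | Left if half are excluded | Left on the strict reading, all treating by mouth |
|---|---|---|---|
| 3% | 15 | 7.5 | 0 |
| 5% | 25 | 12.5 | 0 |
| 10% | 50 | 25 | 0 |
| 20% | 100 | 50 | 0 |

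**4. Precision at such numbers.** If half of those analysed arrive with glucose restored (assumed), the 95% Wilson intervals are:
- 25 of 50: 37% to 63%
- 10 of 20: 30% to 70%
- 5 of 10: 24% to 76%

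These show how little information there is to lose. They do not by themselves measure harm from the exclusions.

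**5. Selection.** Let b be the share of self-treaters excluded, and let p1 and p2 be the proportions restored among the retained and the excluded. The proportion in all self-treaters is (1 − b)p1 + b·p2. The retained group shows p1, so the error is b(p1 − p2). With b = 50%, p1 = 90% and p2 = 50%, it is 0.5 × 0.4 = 20 points upward. With p1 and p2 exchanged it is 20 points downward, and with p1 = p2 it is zero. All three inputs are assumptions; the example shows the form of the error and is not an estimate.

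**6. What the listed data can distinguish.** Take one subject who treated an episode and arrives with normal glucose, and another who was never hypoglycemic. Study variables has no item on which they must differ. Past history and awareness describe the patient, not this preparation.

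**The case against.** The strongest reply is that the protocol plans to study self-treatment during the fast, so its exclusions should be read in a way that keeps those subjects. No passage says that taking something for symptoms breaks the fast, and none says that hypoglycemia stops the preparation. This stands in part. A reader might infer that the exclusions remove every self-treater, but the documents do not establish that. They also do not exclude the strict reading, and staff could classify the same subject differently while following the text.

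Second, the questionnaire may already ask about episodes and self-treatment. That is possible. The point is that these items are not listed, not that they are known to be uncollected. Even if they are asked, no analysis set is stated for the objective.

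Third, the exclusions are not the only obstacle. With no glucose at the time of the episode, sufficiency of self-treatment cannot be proved even if nobody is excluded. This stands, and it limits what any fix can deliver.

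Fourth, a completers-only primary percentage is a legitimate target under Objectives. Agreed. A reader might still infer that this percentage is biased, but the documents do not support a direction. Suppose 50 of 1000 are abnormal on arrival and 25 subjects are excluded. If all 25 were abnormal, the completers show 25/975 = 2.6%. If all 25 had recovered, they show 50/975 = 5.1%. The documents do not say which is nearer.

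**Conclusion.** The concern holds for the second secondary objective only. As written, the plan can lose an unknown share of self-treaters through exclusions decided after the event. That share runs from none to all who took something by mouth, depending on definitions the protocol does not give. With the listed variables alone, those who remain and have recovered cannot be identified. The objective would then be unanswerable, or answered in a group selected on the event itself.

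The counts in the working rest on an assumed 50% self-treatment share, and the selection example rests wholly on assumed inputs. The primary percentage, the risk-factor models and the figure of 1000 are not called into question. This should be fixed before data collection, because unrecorded episodes cannot be reliably recovered afterwards.

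**What to change.** None of these changes alters clinical management.

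1. Apply exclusions 2 and 3 as analysis-set rules for the primary percentage and the risk-factor models, not as eligibility rules, so that data are kept on deviators who have a glucose value before colonoscopy. State, for analysis, what counts as a breach of the fast, as incomplete preparation and as self-treatment. State that the 1000 counts subjects in the completers set.
2. Add three items to the existing questionnaire and to Study variables: hypoglycemic episode during this preparation, self-treatment taken, and reason for any deviation.
3. Analyse the second secondary objective in all subjects who report an episode and self-treatment and have a pre-colonoscopy glucose, whether or not they broke the fast or finished the preparation. Report the numbers below 70 mg/dL, from 70 to 250 mg/dL and above 250 mg/dL (the protocol's own cut-offs) with a confidence interval. Describe them as self-reported episodes with glucose on arrival, not as proof that self-treatment caused recovery.
4. Report exclusion counts by reason.

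The completers-only primary percentage stays. A sensitivity analysis that retains all deviators is optional. It could not cover cancelled procedures, because inclusion requires that the colonoscopy took place.

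The cost is protocol wording, three questionnaire items, an exclusion log and one further analysis set, with no extra visits or tests. If the 1000 counts completers, somewhat more than 1000 people will have data recorded. The result will probably rest on few subjects and on self-report, with no glucose at the time of the episode.

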## **Subject numbers**

The incidence of abnormal glucose levels is expected to be between 5 to 10%. 50 positive subjects are required for multivariable analysis, therefore 1000 subjects should be included in this study.

## **Study design**

1. Colonoscopy preparation

- ① Subjects will be instructed to fast from 6pm of the day before colonoscopy.
- ② Subjects will be instructed to abstain from diabetes medication while the subjects fast.
- ③ Subjects who are scheduled to undergo colonoscopy in the morning will take colonoscopy preparation medication (2L (liter) of polyethylene glycol with ascorbic acid) in a split dose (i.e. 1L from 8-10 pm of the day before colonoscopy and 1L 4-6 hours before colonoscopy). Those who will undergo colonoscopy in the afternoon will take 2L of the preparation medication 6 hours before colonoscopy.

- ④ Subjects will be instructed to take the preparation medication at rate of 250 mL every 10 to 15 minutes.

## 2. Confirmation of diabetes

- ① Diabetes history will be rechecked by a trained nurse who is blind to the study at the preparation room of the endoscopy center.
- ② Subjects will fill out a questionnaire and have their plasma glucose checked while awaiting colonoscopy.

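### The primary endpoint is a prevalence at one pre-colonoscopy glucose reading, but the plan words it as an incidence and aims at the whole preparation period

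*Combined protocol and SAP*

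**What the plan says.** The primary objective (Objectives) is "To discover the incidence of abnormal glucose levels after fasting and bowel preparation for colonoscopy in type 2 diabetes subjects". The Background gives a different time frame: "we aim to investigate the occurrence of abnormal blood glucose levels in diabetes patients during colonoscopy preparation". The second secondary objective is "Find out if self-treatment is sufficient to treat hypoglycemia which occurs during fasting and bowel preparation", so the plan expects some subjects to go low, and to treat it, before they reach the endoscopy center.

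The measurement is described under 2. Confirmation of diabetes: subjects complete a questionnaire and "have their plasma glucose checked while awaiting colonoscopy". In Study variables the only glucose value is "Plasma glucose level before colonoscopy". Section 3, Treatment of abnormal glucose levels, mentions a later check, but only to decide discharge after treatment.

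The Statistical Analysis section defines the primary endpoint as the percentage of subjects with either abnormality. It gives no time point, data source or cut-off. The figures <70 and >250 mg/dL appear only in the treatment section.

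**The concern.** One reading per subject, with no earlier value to compare it with, shows who is abnormal at that moment. It does not show who became abnormal over the preceding hours. The plan itself gives reasons why the two may differ: self-treated lows (Objectives), "abnormal glucose levels due to Dawn phenomenon or Somogyi effect" (Background), and reduced recognition of symptoms through autonomic dysfunction (Background).

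What is at stake is the conclusion. A small percentage at the reading, reported as an incidence, could be taken to mean that fasting and bowel preparation seldom cause hypoglycemia. The measurement supports a narrower statement, about the state of subjects just before the procedure.

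**Working it through.** **1. The plan's own figure.** Subject numbers expects a rate of 5 to 10% and requires 50 positive subjects. 50 / 0.05 = 1000, which is the stated size (at 10%, 50 / 0.10 = 500). The figure reproduces and is not in dispute. That section also calls the rate an incidence and gives no time window.

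**2. The unobserved window.** Study design: "Subjects will be instructed to fast from 6pm of the day before colonoscopy". Background: "Subjects normally undergo 14-20 hours of fasting before colonoscopy". Counting from 6 pm, 14 hours ends at 8 am and 20 hours at 2 pm. No glucose variable covers those hours. The 14-20 hours is a Background description; the design fixes only the start.

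**3. Where an earlier low ends up.** Assume the treatment thresholds are also the endpoint cut-offs.

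| Course after a low during the fast | At the pre-colonoscopy reading | Composite endpoint | Hypo/hyper split |
|---|---|---|---|
| a: low again or still low | <70 | counted | correct |
| b: rebounds high | >250 | counted | recorded as hyperglycemia |
| c: corrected or rebounds to normal | 70-250 | missed | missed |
| d: broke the fast with sugar and is excluded (Subjects, third exclusion criterion) | not analysed | outside numerator and denominator | outside |

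**4. Direction.** Let N be all subjects eligible apart from the fasting criterion, and let a (here including subjects low only at the reading), b, c and d be counts.

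- Hypoglycemia at the reading: a / (N − d).
- Hypoglycemia at any time in the fast: (a + b + c + d) / N.
- Because a ≤ N − d, we have a / (N − d) ≤ (a + d) / N ≤ (a + b + c + d) / N. The reading cannot exceed the any-time figure for hypoglycemia, and they are equal only if no episode falls in b or c and none is lost through d.
- For the composite, b drops out of the shortfall. If nobody is excluded (d = 0), lows missed by the composite amount to c / N.
- Without a baseline, a subject already above 250 mg/dL before the fast counts as positive. The sign of the difference between the composite and an incidence of new abnormality is therefore open.

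**5. Size.** The documents give none of b, c or d, so no under-count can be computed. As a yardstick only, the 95% half-width at N = 1000 is 1.96 × √(p(1 − p)/1000):

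- p = 5%: 1.96 × √(0.05 × 0.95 / 1000) = 1.35 percentage points, or 13.5 subjects.
- p = 10%: 1.96 × √(0.10 × 0.90 / 1000) = 1.86 percentage points, or 18.6 subjects.

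About 14 to 19 subjects in group c would thus shift the composite by as much as its sampling error. More subjects would shrink the sampling error but not the shift.

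**The case against.** The strongest reply is that the formal primary objective places the abnormality after fasting and preparation, and a reading taken while waiting for the procedure does just that. The endpoint is stated as a percentage, not a rate over an interval, and the during-preparation wording is Background prose. The Background also says that 14-17 hours of fasting lowers glucose by 20-40%, which is a reason to measure at the end. This stands: the reading is a legitimate measure of the state it observes. It does not rescue the word incidence, and two time frames remain in one document.

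A second reply is that the questionnaire may already ask about episodes in the fast, since the self-treatment endpoint needs that information. Its content is not described. The variable list names only past episodes and awareness of hypoglycemia, and nothing says that events in this fast count toward any percentage. That the form asks about them is possible but not documented.

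A third reply is that the proposed items rely on recall, which the plan itself says may be impaired, and on home meters that it does not provide. This stands too. It is why the result should be supplementary.

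Two stronger readings are tempting and lack support. A reader might infer that the primary percentage is understated by a known fraction, for instance by scaling down the 5% or the 20% hypoglycemia rate cited in the Background. The 5% is the lower bound for all abnormal glucose, not for hypoglycemia. The plan does not say whether the 20% was a rate over the fast or itself a pre-procedure reading. No document gives the share of lows resolved by then. A reader might also infer that every rebound lowers the primary percentage. A rebound above 250 mg/dL does not.

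**Conclusion.** The point holds as one of definition and ascertainment. The primary endpoint estimates the prevalence of hypo- or hyperglycemia at the pre-colonoscopy reading. It agrees with the timing in the primary objective, but not with the word incidence or with the Background aim. Lows that occurred and returned to normal earlier in the fast are not captured by the reading, and no listed variable records them. Subjects who took sugar for a low may also be lost through the fasting exclusion; the plan does not say how they are handled.

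For hypoglycemia alone, the reading can only equal or fall below the any-time percentage. The size of the gap is not derivable. The 14 to 19 subjects per 1000 is a yardstick against sampling error, not an estimate. It assumes 1000 analysed subjects and 5 to 10% abnormal at the reading. The table and direction argument assume that the treatment thresholds define the endpoint.

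The measurement remains usable once correctly labelled, so this is a cheap improvement, not a flaw that invalidates the primary result.

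**What to change.** 1. In Objectives and Statistical Analysis, define the primary endpoint as the percentage of subjects with hypo- or hyperglycemia at the pre-colonoscopy reading. Reconcile the Objectives with the Background so that the conclusion is limited to that time point.
2. Add items to the existing questionnaire covering the time since 6 pm on the previous day: hypoglycemic symptoms, any home glucose reading <70 mg/dL, and any self-treatment.
3. Report, as a supplementary result, the percentage with hypoglycemia at any time in the fast (pre-colonoscopy reading or reported event), with symptom-only events shown separately. Include in its numerator and denominator the subjects who broke the fast to self-treat, even if the fasting criterion removes them from the primary analysis.

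The cost is a few sentences of protocol text, some questions on a form already in use, and one extra reported percentage. The downside is that self-report is softer than a plasma value and will miss unrecognised episodes, including a silent overnight low. The primary figure does not change; its interpretation does.
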